The goal of these pilot studies is to investigate whether disrupting fear reconsolidation with propranolol HCI in adult OCD and SAD patients is feasible and leads to a reduction in OCD and SAD symptoms and an improvement in a Behavioral Avoidance Task (BAT).

Description of Subject Population

Sample #1

Specify subject population

Adult individuals with OCD

Number of completers required to accomplish study aims

20

Projected number of subjects who will be enrolled to obtain required number of completers

25

Age range of subject population

18-60

Sample #2

Specify subject population

Adult individuals with public speaking fears and SAD, performance only type

Number of completers required to accomplish study aims

20

Projected number of subjects who will be enrolled to obtain required number of completers

25

Age range of subject population

18-60

Gender, Racial and Ethnic Breakdown

Based on the community from which we will be drawing patients and proportions to those encountered during previous clinical trials at this site, we expect the sample to be approximately 5% Hispanic and 95% Non-Hispanic; racially there will be 89% White, 9% Black, 2% Asian. Based upon the prevalence of OCD, it is expected that the sample will be approximately 1:1 =male:female.

Description of subject population

Females and male adults with a diagnosis of OCD or SAD (performance only type) and clinically significant symptoms of OCD or fear of public speaking.

All ethno-racial groups will be recruited.

Recruitment Procedures

Describe settings where recruitment will occur

Recruitment will draw from the broadest possible population with respect to gender and ethnic origin. Participants will be enrolled through the Anxiety Disorders Clinic, located on the third floor of the New York State Psychiatric Institute.

How and by whom will subjects be approached and/or recruited?

OCD and SAD patients will be recruited by physician or mental health practitioner referrals, or patient or

family referrals following advertisement of our work.

How will the study be advertised/publicized?

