Select the names of persons designated to obtain consent/assent 2
[name], MD
[name], MD
[name], MD
Type in the name(s) not found in the above list

Study Procedures

Describe the procedures required for this study

VISIT 1. Screening/evaluation for eligibility (conducted under IRB #6112R - Anxiety Disorders Clinic and Hispanic Treatment Program Screening and evaluation Process) and study consent followed by BAT.

Patients deemed eligible following phone screening will undergo with their written consent: 1) a clinical interview by a senior clinician (M.D. or Ph.D.) that will include a MINI for DSM-5; 2) a physical examination (i.e., history, physical, EKG test, and urine pregnancy test [for females]) by an MD; ; and 3a) for OCD patients a Y-BOCS for OCD severity; 3b) for SAD patients LSAS and PRCS for SAD and public speaking fear severity; 4) and HDRS to assess depression severity. ; and 5) a personalized Behavioral Avoidance Task (BAT) by a trained rater. Those who meet entry criteria will provide written informed consent for this study and then complete a personalized Behavioral Avoidance Task (BAT) by a trained rater. The BAT for OCD patients will assess degree of fear (using a subjective 0-100 scale) and overt approach behavior while being exposed to an OCD trigger (e.g. a toilet in patients with contamination fears). For SAD patients it will assess fear during a brief speech task. Following this procedure, participants will be dismissed for the day and they will be re-contacted to schedule visit 2 once their EKG and blood results come back and it is confirmed that they are eligible to complete the study.

Those who meet entry criteria will provide written informed consent for this study and then enter the baseline assessment and intervention.

VISIT 2. Consent, Baseline assessment (independent evaluator) and intervention

Consent and Baseline Assessment: After participants have signed consent, An independent evaluator will assess global psychopathology (CGI); depressive symptoms (HDRS); and anxiety symptoms (DASS). OCD patients will also be assessed for OCD symptoms (YBOCS), and

Protocol Summary Form 7293 [name]

SAD patients will also be assessed for SAD (LSAS) and fear of public speaking (PRCS). Then participants within each disorder will be randomized to one of two groups. Randomized assignments will be generated using a random number generator in SPSS using a block design.

Intervention:

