OCD participants will receive a short exposure (2') to an OCD phobic stimulus trigger (e.g. a toilet). SAD participants will be asked to prepare and give a short (2 minute) speech before an audience of several staff members. These exposures will be conducted by either a psychologist or psychiatrist on the study team.

After that, half of the OCD participants and half of the SAD participants will receive a single oral dose of propranolol HCI 40 mg. The other half of participants (within each diagnostic group) will receive a placebo. Following the administration of the propanolol or placebo participants will be asked to wait in the Anxiety Disorders Clinic for 90'. The participant's blood pressure, heart rate, and possible side effects will be assessed (using a side-effects checklist) at three time points: before the short exposure, after the administration of the propranolol/placebo, and after the 90' waiting period. Participants will be told that the intervention they have received may help them overcome their fears during the following 2 weeks. They will be asked to keep a daily record of their avoidance/approach behaviors (for OCD patients, using the avoidance item from the self-report YBOCS). OCD participants will be also asked to assess daily their OC symptoms using two visual separate visual analogue scales (VAS), one for obsessions and one for compulsions. SAD participants will assess their public speaking fears daily using a VAS for anxiety and a VAS for avoidance.

Follow-up (independent evaluator)

After 1 week, participants will be contacted on the phone by the independent evaluator to assess depressive, and anxiety symptoms during the past week (using the HDRS-17, DASS, and CGI). OCD patients will also complete the YBOCS, and SAD patients will complete the LSAS and PRCS.

VISIT 3. Final assessment (independent evaluator)

After 14 days, participants will be assessed in our clinic by the independent evaluator with the same instruments (i.e., YBOCS, LSAS, PRCS, HDRS-17, DASS, and CGI) used in the baseline. In addition, the BAT conducted at screening will be repeated to measure any change in avoidance. The daily records of OC avoidance/approach behaviors as well as their VAS will then be collected.

You can upload charts or diagrams if any

Criteria for Early Discontinuation

Criteria for Early Discontinuation

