- Clinical Global impression (CGI, 1 minute). This is a clinician rated instrument for rating global psychopathological severity.
- 17-Item Hamilton Depression Rating Scale (HDRS-17, 5 minutes). This is a clinician rated instrument for rating depression.
- Depression Anxiety Stress Scale (DASS, 5 minutes). A self-report of anxiety and depressive symptoms.
- Behavioral Avoidance Test for Obsessive-Compulsive Disorder (BAT-OCD, 15 minutes). This is a structured instrument, which has been previously used (Steketee et al., 1996) to assess changes in OCD symptoms and approach behaviors.
- Subject unit of distress scale (1 min) will be used during the SAD BAT to rate intensity of anxiety on a 100 point scale.
- Side Effect Checklist (SECL, 3 minutes): Side Effect Assessment: possible side effects will be rated on a scale from 0 (none) to 3 (severe).
- Visual analogue scales for obsessions and compulsions (VAS-OCD, 1 minute)
- Visual analogue scales for public speaking anxiety and avoidance (VAS-SAD, 1 minute)
- Self-report of OCD-related avoidance (avoidance item of self-report YBOCS, 1 minute)

Please attach copies, unless standard instruments are used

Off label and investigational use of drugs/devices

Choose from the following that will be applicable to your study

✓ Drug

Select the number of drugs used in this study

1

Drug #1

Name of the drug Propanolol Manufacturer and other information

It is available generically from several manufacturers.

Approval Status

No IND is required

Choose one of the following options

FDA conditions are met (see 'Rules')

Explain

The investigation is not intended to be reported to the FDA in support of a new indication or any significant change in labeling. The drug is marketed. The investigation is not intended to support a change in advertising. It uses a standard route of administration and dosage in a low risk patient population.

Research Related Delay to Treatment

Will research procedures result in a delay to treatment?

Yes

Maximum duration of delay to any treatment

Two weeks

Maximum duration of delay to standard care or treatment of known efficacy

This study is two weeks long and during this period the participant is asked not to seek additional treatment. Some OCD patients may be on a stable dose of an SRI. For these individuals, they will already be receiving a treatment of known efficacy for OCD.

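### The daily VAS and avoidance records have no pre-dose rating, so these supplementary measures cannot show change from pre-dose or be adjusted for their own baseline; the cost is precision and interpretability, not validity

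*Combined protocol and SAP*

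**What the plan says.** The daily self-ratings appear in the Intervention part of Visit 2, after the exposure, the single dose, the 90-minute wait and the statement to participants that the intervention may help over the next 2 weeks.

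- Avoidance: "They will be asked to keep a daily record of their avoidance/approach behaviors (for OCD patients, using the avoidance item from the self-report YBOCS".
- OCD symptoms: "OCD participants will be also asked to assess daily their OC symptoms using two visual separate visual analogue scales (VAS", one scale for obsessions and one for compulsions.
- SAD: "SAD participants will assess their public speaking fears daily using a VAS for anxiety and a VAS for avoidance".

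The records are collected at Visit 3.

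The pre-dose assessments are listed separately. Visit 1 has the MINI, physical examination, Y-BOCS (OCD) or LSAS and PRCS (SAD), HDRS and the BAT. For the Visit 2 baseline, "An independent evaluator will assess global psychopathology (CGI); depressive symptoms (HDRS); and anxiety symptoms (DASS"; then "OCD patients will also be assessed for OCD symptoms (YBOCS), and" and "SAD patients will also be assessed for SAD (LSAS) and fear of public speaking (PRCS". Neither visit includes a VAS or the self-report avoidance item. Assessment Instruments lists them (for example "Visual analogue scales for obsessions and compulsions (VAS-OCD, 1 minute") without timing. The Visit 3 list of scales repeated from baseline omits them too.

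Specific Aims asks whether the intervention is feasible, whether it "leads to a reduction in OCD and SAD symptoms", and whether it improves the BAT. The daily records are not named there, and no analysis is given for them.

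**The concern.** The daily records are the most frequent measurements in the trial and the only ones with day-by-day resolution. Their first entry already follows the exposure, the dose and the expectancy statement, so it is not a baseline.

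Three things are lost. Change from pre-dose cannot be computed on these scales. The arm comparison cannot be adjusted for each person's own starting level on the same scale, which matters with about 10 per arm. And if the effect is abrupt, much of it may precede the first entry, so a slope from day 1 would not show it. An abrupt effect is not far-fetched here: the reference list includes a study of phobic behaviour whose title describes the change that way.

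**Working it through.** **Inputs.** Description of Subject Population gives 20 completers per disorder. Study Procedures allocates half to each arm, so 10 per arm. The protocol gives no alpha, effect size, SD or pre/post correlation, and no calculation on this point to reproduce. Assumed below: two-sided alpha 0.05 and a correlation rho of 0.3, 0.5 or 0.7 between a pre-dose rating and the post-dose rating.

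**Chance imbalance at baseline.** In outcome SD units, the SD of the arm difference is sqrt(2/10) = 0.447. The probability that it exceeds 0.5 SD either way is 2 × (1 − Phi(0.5/0.447)) = 0.26. An imbalance of 0.45 SD shifts the unadjusted post-dose contrast by rho × 0.447 = 0.13, 0.22 and 0.31 SD for the three correlations. The 26% is the frequency of an imbalance, not of a wrong conclusion.

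**Validity without a baseline.** In 20,000 simulated null trials with 10 per arm and rho = 0.6, the unadjusted post-dose t-test rejected in 5.1%. Chance imbalance is already allowed for in its standard error.

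**Precision gained from a same-scale baseline.** Adjustment multiplies the residual variance by 1 − rho². Estimating the covariate slope with 20 people multiplies the expected variance by 1 + 1/(20 − 4) = 1.0625. The net standard-error ratio is sqrt((1 − rho²) × 1.0625).

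| rho | 1 − rho² | × 1.0625 | SE ratio | SE reduction |
|---|---|---|---|---|
| 0.3 | 0.91 | 0.967 | 0.983 | 1.7% |
| 0.5 | 0.75 | 0.797 | 0.893 | 11% |
| 0.7 | 0.51 | 0.542 | 0.736 | 26% |

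In power terms, for a 1.0 SD effect (noncentral t), the post-only comparison has 0.56. With the covariate it has 0.60, 0.68 and 0.84 at rho = 0.3, 0.5 and 0.7. These adjusted figures allow for the lost degree of freedom but not the 1.0625 factor, so they are slightly optimistic.

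**The sample actually collected.** The progress report gives 7 SAD participants and no arm split. If split 4 and 3 (assumption), the imbalance SD is sqrt(1/4 + 1/3) = 0.76, and the probability of exceeding 0.5 SD is about 51%. The slope-estimation factor becomes 1 + 1/(7 − 4) = 1.33. At rho = 0.5 the net variance factor is 0.75 × 1.33 = 1.00, so adjustment gains nothing; at rho = 0.3 it is 0.91 × 1.33 = 1.21, a loss.

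**The case against.** The strongest reply is that these are supplementary measures and that everything serving the aim has a baseline. This stands. Y-BOCS, LSAS and PRCS are taken before the dose and repeated at week 1 and day 14; the BAT is done at Visit 1 and repeated at Visit 3. Avoidance is not without a pre-dose measure either: the LSAS rates fear and avoidance, and the BAT is repeated to measure change in avoidance.

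A reader might infer three stronger things that the documents do not support.

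- *That an arm difference on the daily records could not be attributed to treatment.* Allocation is randomised within disorder, and the exposure and expectancy statement apply to both arms. The post-dose comparison is valid, and it could still detect an abrupt effect, with less precision.
- *That no within-person change can be reported.* Roughly 14 daily entries give change from day 1 and a difference in slope between arms. Only change from pre-dose is missing.
- *That no baseline adjustment is possible.* Y-BOCS, LSAS, PRCS and the Visit 1 BAT can be used as covariates. The gain would probably be smaller than from the same scale, and they cannot supply change on the VAS. In SAD the LSAS may be a weak proxy: it covers 24 situations, the sample has performance-only fears, and a score above 60 is tied to exclusion, which narrows its range.

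The 11% to 26% gain is also measured against no adjustment at all. Against a proxy-adjusted analysis it would be smaller, by an amount the documents do not allow one to calculate.

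**Conclusion.** The point holds for the daily records only. No pre-dose value is scheduled on these scales, so change from pre-dose and same-scale adjustment are not available. The loss is in precision and interpretability; neither the validity of the randomised comparison nor the outcomes named in the aim are affected.

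The size depends almost entirely on the correlation, which is assumed: worthwhile at 0.5 to 0.7, negligible at 0.3. This is a low-cost improvement rather than a serious flaw. It is worth making because the trial already asks participants for two weeks of daily ratings and pays $25 for them, and because this pilot is meant to support a larger trial.

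**What to change.** At Visit 2, before the exposure, have each participant complete once the same VAS used in the daily record, plus the self-report Y-BOCS avoidance item in OCD. State how the daily records will be analysed, for example as arm differences in post-dose level adjusted for that pre-dose rating.

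Assessment Instruments gives 1 minute for each VAS set and 1 minute for the avoidance item, so the added burden is about 2 minutes in OCD and 1 minute in SAD. No new instrument, visit or staff is needed. A run-in diary between Visits 1 and 2 would give several pre-dose days, but it is optional and less clearly cheap: the length of that wait is not stated, consent is described at both visits, and the paid diary task would change.

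The progress report says recruitment fell short and the small sample is being analysed, so past participants cannot gain a baseline. For them, report post-dose levels adjusted for the corresponding pre-dose clinic scale (Y-BOCS in OCD; LSAS or PRCS in SAD), and do not describe the daily records as change from baseline. Show the unadjusted levels alongside: with 7 SAD participants, adjustment gains precision only if the proxy's correlation with the daily rating exceeds about 0.5. Carry the pre-dose rating into the future trial.

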Proven obsessive-compulsive disorder (OCD) and social anxiety disorder (SAD) treatments include medications called serotonin reuptake inhibitors (SRIs) and cognitive-behavioral therapy (CBT). However, up to half of OCD and SAD patients do not achieve wellness from these treatments. Thus, new treatments are needed.

This study will examine the efficacy of disrupting fear reconsolidation with propranolol hydrochloride (HCI), a method recently found effective in adults with spider fears but not yet tested in OCD or SAD, in 2 pilot randomized controlled trials (one in OCD, one in SAD).

A total of 20 adults with OCD, and 20 adults with SAD, between the ages of 18 and 60 years will participate in the study.

Background, Significance and Rationale

Background, Significance and Rationale

The two first-line treatments for OCD and SAD are a class of medications called serotonin re-uptake inhibitors (SRIs) and disorder-specific cognitive behavioral therapy. However, up to half of patients with OCD or SAD do not achieve wellness from these treatments.

Recent research suggests that pharmacologically modulating the process of fear memory reconsolidation may be a promising therapeutic avenue in the treatment of fear-related disorders such as OCD and SAD. For example, in a spider phobic sample, Soeter and Kindt (2016) administered 40mg of propranolol HCI after reactivating spider fear (by presenting a tarantula for 2 minutes) to disrupt reconsolidation of the fear memory. Participants who received propanolol HCI had reduced fear at two-week follow up compared to participants who received placebo. One year later, the benefits were maintained.

We propose two small pilot randomized placebo-controlled trial to test whether disrupting fear reconsolidation using propranolol HCI in adult OCD and SAD patients leads to a significant reduction in OCD and SAD symptoms and a significant improvement in a standardized behavioral avoidance test (BAT). We will study the subgroup of SAD patients with performance only fears related to public speaking, because these circumscribed fears may be most responsive to the treatment tested here. The intent is to collect pilot data on the feasibility, acceptability, and preliminary efficacy of this approach in OCD and SAD patients to support grant application for a future randomized controlled trial with a longer follow-up.

Specific Aims and Hypotheses

Specific Aims and Hypotheses

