Other OCD and all SAD patients will not be on any medications, so the delay to treatment would be the two weeks of the study. Participants will be informed of this delay and offered referrals for treatment at the time of screening if they want immediate treatment.

Treatment to be provided at the end of the study

None as part of this protocol. However, we will make referrals to appropriate accessible treatment settings for participants who desire treatment, and we will follow up to confirm that they have connected with a referral. During the final phone call (one month after the intervention), participants will be assessed on the phone with the YBOCS (OCD participants) or LSAS (SAD participants). If the original referrals have not worked out, we will provide additional referrals and check if they have worked out.

Clinical Treatment Alternatives

Clinical treatment alternatives

Subjects do not have to participate in this study to receive treatment for OCD of SAD. There are two evidence-based first-line treatments for OCD and SAD. The first is a class of medications called *Serotonin*

Reuptake Inhibitors (SRIs). The second is CBT. Subjects will have these treatment options explained to them by the study doctor, and they will be offered the option to receive outside referrals for one or both of these treatments rather than participating in the study.

Risks/Discomforts/Inconveniences

Risks that could be encountered during the study period

Risks associated with propranolol HCI

(Source: Physician Desk Report)

Propranolol hydrochloride is a synthetic beta-adrenergic receptor blocking agent. It is commonly used to treat the following conditions: hypertension, atrial fibrillation, myocardial infarction, migraine, essential tremor, hypertrophic subaortic stenosis, pheochromocytoma, and arrhythmias. Adult dosage for these conditions can be up to 640mg/day.

Propranolol is contraindicated in 1) cardiogenic shock; 2) sinus bradycardia and greater than first degree block; 3) bronchial asthma; and 4) in patients with known hypersensitivity to propranolol hydrochloride. All these conditions are part of the exclusion criteria.

The known side effects of a chronic/prolonged administration of propranolol include bradycardia, CHF, hypotension, lightheadedness, mental depression, N/V, agranulocytosis, and respiratory distress.

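### Should the one-month phone call to social anxiety participants have included the public-speaking scale (PRCS) as well as the LSAS?

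*Combined protocol and SAP*

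**What the plan says.** The Background section restricts the SAD trial to a narrow group: "We will study the subgroup of SAD patients with performance only fears related to public speaking". The Description of Subject Population repeats this for Sample #2: "Adult individuals with public speaking fears and SAD, performance only type". Under Assessment Instruments, the LSAS is a clinician rating of fear and avoidance in 24 situations, and the PRCS is a 30-item self-rating of public-speaking fear.

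Study Procedures pairs the two scales throughout. Visit 1 has "for SAD patients LSAS and PRCS for SAD and public speaking fear severity". The Visit 2 baseline states "SAD patients will also be assessed for SAD (LSAS) and fear of public speaking (PRCS". At one week "participants will be contacted on the phone by the independent evaluator", and SAD patients again complete both. Visit 3, at 14 days, repeats the baseline instruments and the behavioral avoidance test (BAT).

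The one-month call is not in Study Procedures. It appears under Treatment to be provided at the end of the study, an entry that opens by saying the protocol itself provides no treatment. Referrals will be made, and "we will follow up to confirm that they have connected with a referral". Then comes the rating: "participants will be assessed on the phone with the YBOCS (OCD participants) or LSAS (SAD participants". The next sentence offers further referrals if the first did not work out.

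**The concern.** The drug is given after a two-minute speech, to people selected for fear of speaking. A scale spread over 24 social situations is a less specific measure of that fear than one devoted to speaking. The protocol uses both scales four times, including once by phone, so the phone format is no obstacle to the PRCS. At one month the PRCS is absent, and the speech BAT and the daily visual analogue scales (VAS) have also ended, so no speaking-specific measure extends past Day 14.

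The pilot is meant "to support grant application for a future randomized controlled trial with a longer follow-up". If the one-month rating were its evidence on durability, that evidence would rest on the less specific scale, and a flat LSAS might be taken to mean that a benefit on speaking fear had faded.

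**Working it through.** No power, alpha or sample-size figure is involved. The check is a count of instruments, a reading of where the call sits, and a test of the supposed misreading.

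**1. Instruments at each SAD assessment** (Study Procedures; Treatment to be provided at the end of the study)

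| Assessment | LSAS | PRCS | HDRS-17 | DASS | CGI | BAT |
|---|---|---|---|---|---|---|
| Visit 1, screening | yes | yes | yes | no | no | yes |
| Visit 2, baseline | yes | yes | yes | yes | yes | no |
| Week 1, phone | yes | yes | yes | yes | yes | no |
| Visit 3, Day 14 | yes | yes | yes | yes | yes | yes |
| One month, phone | yes | no | no | no | no | no |

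The LSAS is taken at 5 of 5 and the PRCS at 4 of 5, so the factual premise is right. But the depression, anxiety and global scales are absent from the last row too. OCD participants are treated alike: they keep the Y-BOCS and have no BAT, VAS or avoidance item on this call. The pattern is one clinician-rated disorder scale per diagnostic group.

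**2. Status of the call.** Four places agree that it lies outside the outcome assessments.
- Study Procedures ends with Visit 3, which is labelled the final assessment.
- The entry on research-related delay to treatment puts the study's length at two weeks.
- The sentences around the call concern whether referrals succeeded.
- The week-1 contact names the independent evaluator as the assessor; the one-month call names none.

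Specific Aims and Hypotheses asks about feasibility, symptom reduction and the BAT. It does not mention the one-month rating, and no analysis of that rating is described.

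**3. What a reading at that time could show.** Participants are asked to avoid other treatment for 14 days. Taking a month as 28 to 31 days, 28 − 14 = 14 and 31 − 14 = 17, so 14 to 17 days are open to outside treatment, with the team making referrals. That confounds the PRCS as much as the LSAS.

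**4. Could a flat LSAS be misread as lost benefit?** It depends on what it is flat against.
- Flat from Day 14: this reads as stability.
- Back at baseline after a fall by Day 14: the LSAS has risen since Day 14, which is a real change on that scale.
- At baseline, with no fall by Day 14: the LSAS had shown no benefit to lose. The paired LSAS and PRCS values at baseline and Day 14 show whether speaking fear moved while the LSAS did not.

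The misreading therefore requires ignoring data that the trial already collects.

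**5. How many calls it could touch.** The gender counts sum to 5 + 3 = 8, the race counts to 2 + 2 + 3 + 1 = 8 and the ethnicity counts to 1 + 7 = 8. Seven are SAD, which leaves 8 − 7 = 1 OCD. Six have completed, of whom 5 or 6 are SAD, so 7 − 6 = 1 or 7 − 5 = 2 SAD participants had not completed. This assumes that 8 is the enrolled total, because that entry is not legible. The number of calls left is uncertain: a non-completer may have dropped out in an earlier year, and completers counted at Day 14 may still be due a call. Overall Progress says the data are already being analysed.

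**The case for a change.** The best case for the concern comes from the protocol's own mechanism. The risk section states that blocking reconsolidation acts on the reactivated memory and leaves others intact. The reactivated memory here is a speech, so any benefit should concentrate in speaking fear. The eligibility table uses an LSAS score above 60 to help identify SAD that is not performance-only, which treats the LSAS as a marker of breadth. The Background cites benefit maintained at one year in spider phobia, so durability belongs to the rationale. The PRCS is listed at 10 minutes; with the LSAS the call would take 10 + 10 = 20 minutes, against 45 listed for the Y-BOCS.

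All of this shows that the PRCS is the more specific scale and would be cheap to add. That much stands. So does one narrow case: if the LSAS fell by Day 14 and then rose, a PRCS value could help tell whether speaking fear or other situations drove the rise, subject to the confounding by outside treatment. None of it shows that the plan needs this reading. The longer follow-up in the Background describes the future trial; nothing there gives the referral call the task of supplying durability evidence.

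**Conclusion.** The concern does not hold. The PRCS is missing from 1 of 5 SAD ratings, and that rating belongs to a referral check after the two-week study has ended. One disorder scale per diagnostic group is a coherent choice for that purpose. No stated aim, outcome or analysis is affected, and the PRCS is present at every assessment listed in Study Procedures. Adding it would be a preference for one more questionnaire, not a correction.

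This rests on reading the protocol as it is organised: outcome assessments in Study Procedures, ending at Day 14, and the one-month call as part of referral. The aims name no time point, so the reading relies on that structure and on the stated two-week duration. If the one-month rating were later presented as an efficacy result, the choice of scale would matter more, and outside treatment would limit either scale.
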